## Introduction

At present several treadmill scores have been proposed as means for improving the diagnostic accuracy of the exercise treadmill test (ETT) and to predict future risk of cardiac events (Berman et al., 1978 & Do et al., 1997). Although a large number of noninvasive stress testing modalities are currently available, the exercise ECG is still used as a standard for comparison with other clinical and testing risk markers. It is also the least costly of all provocative noninvasive tests. The Duke Treadmill Score (DTS), traditionally a prognostic score, was recently tested as a diagnostic score and shown to predict CAD better than the ST response alone(Shaw et al., 1998). But questions remain regarding the diagnostic accuracy of treadmill scores when applied to a different patient population; furthermore, many treadmill scores have not been compared with one another in the same population(Fearon et al., 2002).To date, no composite stress-test score or noninvasive risk index has been shown to provide both accurate diagnostic and prognostic risk estimates. Despite that exercise treadmill test remains a useful test for diagnosing coronary artery disease (CAD) in patients with chest pain and at intermediate risk for CAD (Do et al., 1997).The sensitivity and specificity of ETT varies considerably. According to a meta-analysis conducted by Gianrossi et al there was a wide variability in sensitivity and specificity of ETT [sensitivity  $68\pm 16\%$  (range 23–100%); specificity  $77\pm 17\%$  (range: 17–100%). Another Meta analysis showed sensitivity of  $81\pm 12\%$  (range: 40–100%) and specificity of  $66\pm 16\%$  (range: 17–100%) (Myers et al., 1994).Fearon WF et al showed sensitivity and specificity was higher when treadmill scores were applied in comparison to ST response alone. They used a consensus score consisting of the Morise, Dentrano and VA score and found predictive accuracy of the consensus score for stratifying patients to low and high likelihood for CAD was significantly higher than the predictive accuracy of DTS, 80(74-86)% versus 71(65-77)% ( $p< 0.0001$ ). But Fearon WF et al conducted the study only on male population in USA and the consensus score was calculated by average of computer generated treadmill scores. In 2012 Mao L et al have shown 73 out of 104 male patients were detected CAD both by ETT and CAG, the accuracy rate was 70.2% which was much higher than that (50.0%) of the female patients ( $p<0.05$ ) and they only used ST changes alone to demonstrate ETT positivity In this study, we will compare the diagnostic accuracy of well known prognostic scores namely, Duke Treadmill Score, Simple Treadmill Score and Cleveland Clinic Score to identify significant coronary artery lesion in Bangladeshi male and female patients.

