## **General Objectives**

To identify difference of predictability of DTS, Simple Treadmill Score and Cleveland Clinic Score to diagnose significant CAD by Coronary Angiography.

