## **Specific Objectives**

1. To estimate accuracy of ST segment response, DTS, Simple Treadmill Score and Cleveland Clinic Score to predict CAD.
2. To compare DTS, Simple treadmill score, Cleveland Clinic Score accuracy to predict coronary artery disease.
3. To identify the relation of different level of treadmill scores with severity of CAD.

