## Statistical Methods

Using angiographic evidence of CAD as the reference, area under the curve (AUC) of receiver operator characteristic (ROC) plots will be determined for the ST response alone and for each treadmill score. The AUC for each treadmill score will be compared with the AUC of the ST response alone and the AUCs of the other treadmill scores. A significant difference is defined as a z-score  $>1.96$ , with  $z\text{-score} = (AUC_1 - AUC_2) / (\text{SE}_1^2 + \text{SE}_2^2)^{1/2}$ . The predictive accuracies of the DTS, the Simple Treadmill Score and Cleveland Clinic Score to stratify patients into high or low likelihood for CAD will be calculated and compared. Test of agreement will be calculated using Kappa statistics. Statistically significant difference between predictive accuracies is defined as a p value  $<0.05$  using the two-tailed Fischer's exact test. Statistical analysis will be performed with the SPSS.

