**Fig: Cleveland Clinic Score Nomogram.**

## Appendix B

### Study design flow chart:

**Patient with Stable chest pain who underwent ETT and admitted for CAG**

**Patient selected according to Inclusion and exclusion criteria**

**DTS, Simple Treadmill Score, Cleveland Clinic score calculated**

**Report collection after CAG**

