### Exercise test variables:

18. Duration of exercise: .....min

19. METs .....

20. Maximum Heart Rate: .....bpm

21. Peak Systolic BP: .....mmHg

22. Maximum ST segment depression: .....mm

23. Exercise induced angina: 0= No angina 1= Non-test limiting

2= Test limiting angina

24. Abnormal heart rate recovery: 0= No 1= Yes

25. Frequent VE during recovery: 0= No 1= Yes

26. Duke Treadmill Score: ..... 0= Low risk

1= High risk

27. Simple Treadmill Score: ..... 0=Low probability

1=High probability

28. Cleveland Clinic Score: ..... 0=Low probability

1= High probability

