### Coronary angiogram:

29. Extent of disease: 0= Normal, 1=SVD, 2=DVD, 3=TVD, 4=LM

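### Fisher's exact test is the stated rule for comparing the accuracies of DTS, STS and CCS, but all three are measured on the same patients and no paired test is planned

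*Combined protocol and SAP*

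**What the plan says.** The second specific objective is "To compare DTS, Simple treadmill score, Cleveland Clinic Score accuracy to predict coronary artery disease"; the general objective is framed in similar terms ("To identify difference of predictability of DTS, Simple Treadmill Score and Cleveland Clinic Score"). Statistical Methods says that the accuracies of the three scores in sorting patients into high or low likelihood of CAD will be calculated and compared. It then gives the decision rule: "Statistically significant difference between predictive accuracies is defined as a p value" below 0.05 "using the two-tailed Fischer's exact test".

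The design is one cross-sectional sample. The Appendix B flow chart has a single stream of patients with the step "DTS, Simple Treadmill Score, Cleveland Clinic score calculated", followed by collection of the angiogram report. The Appendix C form carries all three scores for each patient, with STS and CCS coded from "0=Low probability" to high probability and DTS coded low or high risk. It has one angiographic result: "Extent of disease: 0= Normal, 1=SVD, 2=DVD, 3=TVD, 4=LM".

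The dummy tables cross each score separately with CAD, each with chi-square, Fisher and kappa output. None crosses one score with another.

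**The concern.** Two accuracies from the same 102 patients are not two independent samples of 102. Fisher's test sees only the two totals of correct classifications. The evidence on which score is better lies in the discordant patients, those whom one score classifies correctly and the other does not, and the plan never tabulates them.

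Nothing else in the plan fills the gap:

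- The Fisher rows in the dummy tables test whether one score is associated with CAD. They do not compare two scores.
- Kappa is laid out as score against CAD. It measures agreement, not a difference in accuracy.
- The AUC z-test compares a different quantity, and its standard error also has no covariance term.

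At stake is the accuracy comparison in the second specific objective. If correctness is positively correlated between scores, the planned rule makes a finding of no difference more likely than it should be, and a null result would be hard to interpret. Positive correlation is plausible for DTS and STS, because Appendix A builds both on ST change and exercise angina.

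**Working it through.** **The plan's own figure.** The Sample size calculation uses a one-sample formula with p = 0.55, p1 = 0.71, Zβ = 1.28 and Zα = 1.96:

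[1.28·√(0.55·0.45) + 1.96·√(0.71·0.29)]² / (0.16)² = 90.98, so 91. Then 91/0.90 = 101.1, so 102.

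This reproduces. The 102 was sized for one accuracy against a fixed value, not for score against score.

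**Inputs for the check.**

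- n = 102, with every patient classified by both scores.
- Two-sided 0.05, unadjusted, for both tests.
- Contrast A, 0.71 v 0.80: the only score-versus-score contrast in the documents (Introduction). It compares DTS with a consensus score not studied here, in men only.
- Contrast B, 0.71 v 0.55: the pair of values in the sample size section, used as an illustration.
- Null case: both accuracies 0.71.
- Correlation between scores: **not in the documents**. Assumed latent (bivariate normal) r = −0.3, 0, 0.3, 0.5, 0.7. The resulting correlation of correctness (phi) is about −0.15 to −0.18, 0, 0.17 to 0.18, 0.30 to 0.32, and 0.46 to 0.48, depending on the contrast.

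**Method.** Let p11 be the probability that both scores are correct, from the bivariate normal. The four cells of the paired table are p11, pA − p11, pB − p11 and 1 − pA − pB + p11. All possible tables for n = 102 were enumerated with their multinomial probabilities. Fisher was applied to the two totals as if they came from 102 + 102 separate patients. Exact McNemar was applied to the two discordant counts b and c, with p = 2·P(X ≤ min(b, c)), X ~ Binomial(b + c, ½), capped at 1.

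**Probability of p < 0.05:**

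| Setting | Test | r = −0.3 | 0 | 0.3 | 0.5 | 0.7 |
|---|---|---|---|---|---|---|
| A: 0.71 v 0.80 | Fisher | 28% | 27% | 25% | 23% | 20% |
| | exact McNemar | 24% | 26% | 30% | 35% | 44% |
| B: 0.71 v 0.55 | Fisher | 60% | 61% | 62% | 63% | 65% |
| | exact McNemar | 54% | 61% | 69% | 77% | 86% |
| Equal, 0.71 | Fisher | 5.1% | 3.5% | 2.0% | 1.1% | 0.4% |
| | exact McNemar | 3.7% | 3.5% | 3.2% | 3.0% | 3.0% |

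**If intermediate results are excluded** and only about 70% (71) or 50% (51) of patients are classified by both scores, both tests lose power. For contrast B at r = 0 / 0.3 / 0.5 / 0.7:

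- n = 71: Fisher 43 / 43 / 42 / 41%, exact McNemar 43 / 50 / 58 / 70%.
- n = 51: Fisher 32 / 30 / 29 / 26%, exact McNemar 30 / 36 / 43 / 52%.

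**One data set.** Suppose one score is correct in 72 of 102 patients and another in 82. Fisher gives p = 0.143 whatever the pairing. Exact McNemar gives:

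- 12 discordant patients (11 v 1): p = 0.006
- 20 discordant (15 v 5): p = 0.041
- 24 discordant (17 v 7): p = 0.064

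**Interval width.** The Wald 95% half-width for the difference is 1.96·√{[pA(1−pA) + pB(1−pB) − 2·phi·√(pA(1−pA)·pB(1−pB))]/102}. For contrast A, leaving out the phi term gives 1.96·√[(0.2059 + 0.16)/102] = 11.7 points. Including it at r = 0 / 0.3 / 0.5 / 0.7 gives 11.7 / 10.7 / 9.8 / 8.7 points.

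**The case against.** The strongest reply is that the error is mostly harmless. At zero or positive correlation Fisher does not inflate false positives, at zero it loses nothing against exact McNemar, and at r = −0.3 its error rate is only 5.1%. A significant result under the plan would still be credible. All of this stands.

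The case for positive correlation is also incomplete. Shared inputs correlate the score values, but correctness depends on the cuts as well. Take assumed prevalence 0.6, a sensitive score (sensitivity 0.90, specificity 0.425) and a specific one (0.58, 0.905). Both have accuracy 0.71 (0.6·0.90 + 0.4·0.425; 0.6·0.58 + 0.4·0.905). With latent r = 0.5 within each disease group, overall phi is about −0.02 and the two tests behave alike. Milder mismatch (0.85/0.50 v 0.60/0.875) gives phi of about 0.11. This stands too: the gaps at r = 0.5 to 0.7 show what is possible, not what is expected. Nothing in the documents indicates the correlation for CCS, which enters two of the three pairs.

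Both contrasts are borrowed, and a paired test still has only 26 to 44% power for the 9-point difference at r from 0 to 0.7. The general objective is also served by the AUC comparison, which does not use Fisher.

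These points limit the harm; they do not make an independent-samples test right for paired data. Reading Fisher as meant only for the score-by-CAD tables does not help either, since the second objective would then have no test of accuracy.

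**Conclusion.** The concern holds. The only significance rule stated for comparing the scores' accuracies assumes independent groups, the data are paired by design, and no paired alternative appears in the plan.

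The likely consequence is lost power rather than false positives. At n = 102, replacing Fisher with exact McNemar changes power by about 0 to 21 percentage points for 0.71 v 0.55 and about 0 to 24 points for 0.71 v 0.80 as latent r goes from 0 to 0.7. At r = −0.3 Fisher rejects slightly more often (60 v 54%; 28 v 24%), with an error rate just above nominal. These figures rest on an assumed correlation, illustrative accuracies and every patient being classified by both scores. The defect itself depends on none of them. The sample size is unaffected, and a paired test will not make a 9-point difference well powered.

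It should be corrected before analysis because it concerns a stated objective and costs little.

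**What to change.** In Statistical Methods, replace Fisher's test for between-score accuracy with McNemar's test on the paired correct/incorrect table for each pair of scores. Choose exact or mid-p in advance, and report the accuracy difference with a paired 95% confidence interval. Add three dummy tables (DTS v STS, DTS v CCS, STS v CCS). Keep Fisher in the score-by-CAD tables only as a test of association.

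The paired table also needs a rule for who counts as correct. State in advance how STS results of 40 to 60 and CCS results of 100 to 140 are counted, and which DTS cut applies. Appendix A gives an abnormal cut at +5 and a separate high-risk cut at −10, while the form allows only two codes.

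Optional additions are a multiplicity adjustment over the three pairs and supportive paired comparisons of sensitivity and specificity. If Holm is used, state its cost. At its first step (0.05/3 = 0.0167), for 0.71 v 0.55, n = 102 and r = 0 / 0.3 / 0.5 / 0.7, exact McNemar has 43 / 53 / 62 / 75% power and Fisher at the same level 44 / 43 / 42 / 41%.

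The cost is revised wording, three tables and a sentence on intermediate results. SPSS runs McNemar's test. No new data are needed and the sample size does not change.

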## Dummy Tables/Graphs

### Area Under the Curve

Test Variable(s)	Result	Area	Std. Error a	Asymptotic Sig. b	Asymptotic 95% Confidence Interval	
					Lower Bound	Upper Bound
CCS						
STS						
DTS						

The test result variable(s): CCS, STS, DTS has at least one tie between the positive actual state group and the negative actual state group. Statistics may be biased.

[figure not shown]
a. Under the nonparametric assumption

b. Null hypothesis: true area = 0.5

### DTS \* CAD

#### Crosstab Count

	CAD		Total
	No CAD	NCAD	
Low likelihood			
High Likelihood			
Total			

### Chi-Square Tests

	Value	Df	Asymp. Sig. (2-sided)	Sig. ExactSig. (2-sided)	Exact Sig. (1-sided)
Pearson Chi-Square					
Continuity Correction b					
Likelihood Ratio					
Fisher's Exact Test					
Linear-by-Linear Association					
N of Valid Cases					

a. 1 cells (25.0%) have expected count less than 5. The minimum expected count is 2.74.

b. Computed only for a 2x2 table

### Symmetric Measures

	value	Asymp. Error a	Std. Approx. T b	Approx. Sig.
Measure of Agreement	Kappa			
N of Valid Cases				

[figure not shown]
a. Not assuming the null hypothesis.

b. Using the asymptotic standard error assuming the null hypothesis.

## STS \* CAD

### Crosstab Count

	CAD		Total
	No CAD	CAD	
Low likelihood			
High likelihood			

### Chi-Square Tests

	Value	Df	Asymp. Sig. (2-sided)	Exact Sig. (2-sided)	Exact Sig. (1-sided)
Pearson Chi-Square Continuity Correction b Likelihood Ratio Fisher's Exact Test Linear-by-Linear Association N of Valid Cases					

a. 1 cells (25.0%) have expected count less than 5. The minimum expected count is 3.06.

b. Computed only for a 2x2 table

### Symmetric Measures

	Value	Asymp. Std. Error a	Approx. T b	Approx. Sig.
Measure of Agreement N of Valid Cases	Kappa			

[figure not shown]
a. Not assuming the null hypothesis.

b. Using the asymptotic standard error assuming the null hypothesis.

## CCS \* CAD

### Crosstab Count

	CAD		Total
	No CAD	CAD	
CC Low likelihood			
S High Likelihood			
Total			

### Chi-Square Tests

	Value	df	Asymp. Sig. (2-sided)	Exact Sig. (2-sided)	Exact Sig. (1-sided)
Pearson Chi-Square					
Continuity Correction b					
Likelihood Ratio					
Fisher's Exact Test					
Linear-by-Linear Association					
N of Valid Cases					

a. 1 cells (25.0%) have expected count less than 5. The minimum expected count is 3.54.

b. Computed only for a 2x2 table

### Symmetric Measures

	Value	Asymp. Std. Error a	Approx. T b	Approx. Sig.
Measure of Agreement	Kappa			
N of Valid Cases				

a. Not assuming the null hypothesis.

b. Using the asymptotic standard error assuming the null hypothesis.

## Operational Definitions

### Stable IHD

Stable IHD is defined as stable angina if there is no substantial change in symptoms over several weeks. It is usually characterized by episodes of reversible myocardial supply-demand mismatch, related to ischemia or hypoxia, which may be inducible by exercise, emotion or other stress and reproducible—but, which may also be occurring spontaneously. Stable angina has duration less than 20 mins and relieved by taking rest or sublingual nitroglycerine. (Partick et al., 1999)

Chest pain is defined as “typical angina” if it consists of characteristic (1) substernal discomfort, (2) is provoked by stress, and (3) is relieved by rest or nitroglycerin. It is considered “atypical” if it involves two or less of the previously mentioned criteria. It is labeled as non-cardiac chest pain if only one or none of the above three characters is present. (Griffin 2013)

### STEMI

New ST elevation at the J point in at least 2 contiguous leads of  $\geq 2$  mm (0.2 mV) in men or  $\geq 1.5$  mm (0.15 mV) in women in leads  $V_2-V_3$  and/or of  $\geq 1$  mm (0.1 mV) in other contiguous chest leads or the limb leads (Thygesen et al., 2012).

The majority of patients will evolve ECG evidence of Q-wave infarction. New or presumably new LBBB has been considered a STEMI equivalent. Most cases of LBBB at time of presentation, however, are “not known to be old” because of prior electrocardiogram (ECG) is not available for comparison. New or presumably new LBBB at presentation occurs infrequently, may interfere with ST-elevation analysis, and should not be considered diagnostic of acute myocardial infarction (MI) in isolation .Criteria for ECG diagnosis of acute STEMI in the setting of LBBB have been proposed . Baseline ECG abnormalities other than LBBB (e.g., paced rhythm, LV hypertrophy, Brugada syndrome) may obscure interpretation. In addition, ST depression in  $\geq 2$  precordial leads ( $V_1-V_4$ ) may indicate transmural posterior injury; multilead ST depression with coexistent ST elevation in lead aVR has been described in patients with left main or proximal left anterior descending artery occlusion . Rarely, hyperacute T-wave changes

may be observed in the very early phase of STEMI, before the development of ST elevation (Patrick et al., 2013).

### Acute MI

The classic world health organization (WHO) criteria for an acute MI require that two of the following three elements be present (Thygesen et al., 2012).

- i. A history suggestive of coronary ischemia for a prolonged period of time (> 30 minutes)
- ii. Evolutionary changes on serial ECGs suggestive of MI and
- iii. A rise and fall in serum cardiac markers consistent with myonecrosis

### UNSTABLE ANGINA/NSTEMI

Unstable angina (UA) and non-ST-segment elevation myocardial infarction (NSTEMI) remain leading causes of morbidity and mortality in the United States. These conditions are part of a continuum of acute coronary syndromes (ACSs) that range from UA and NSTEMI to ST-segment elevation myocardial infarction (STEMI). The clinical presentation of non-ST-elevation acute coronary syndrome (NSTE-ACS) can be variable, ranging from progressive exertional angina to postinfarction angina.

#### **Braunwald classification of unstable angina** (Griffin 2013)

Class	Clinical Characteristics		
I	Exertional	angina	
	New onset, severe, or accelerated, Angina of < 2 moduration,More frequent angina,Angina precipitated by less exertion, No rest angina in the last 2 mo		
II	Rest	angina,	subacute
	Rest angina within the last month but none within 48 h of presentation		
III	Rest	angina,	acute
	Rest angina within 48 h of presentation		

Clinical Circumstances			
A	Secondary Caused by a noncardiac condition, such as anemia, infection, thyrotoxicosis, or hypoxemia	unstable	angina
B	Primary unstable angina		
C	Postinfarction Within 2 wk of documented myocardial infarction	unstable	angina

Because NSTEMI is distinguished from UA by the presence of elevated serum levels of cardiac biomarkers, serial measurements in patients presenting with ACS should be performed. With improvements in the diagnosis and risk stratification of patients with UA and NSTEMI, therapeutic approaches to NSTE-ACS have continued to evolve (Griffin 2013).

#### DIABETES MELLITUS(ADA Guideline, Jan 2016)

Diabetes is a group of metabolic diseases characterized by hyperglycemia resulting from defects in insulin secretion, insulin action, or both. Diabetes mellitus is defined by  $\text{HbA1C} \geq 6.5\%$  or fasting plasma glucose of 7.0 mmol/L or above, or post-prandial plasma glucose of 11.1 mmol/L or above with symptoms of hyperglycemia. An abnormal oral glucose tolerance test done recently or previously diagnosed as DM by a physician with or without on antidiabetic medication are also considered as diabetic patient.

#### SMOKING(Cannon, et al., 2001 )

History of confirmed cigarette smoking in the past or in recent days is classified as following categories-

1. Current: Smoking cigarettes within 1 month of this admission.
2. Recent: Stopped smoking cigarettes between 1 month and 1 year before this admission.
3. Former: Stopped smoking cigarettes more than 1 year before this admission.
4. Never: Never smoked cigarettes.

## HYPERTENSION (Whelton et al., 2017)

Sustained elevation of systolic and/or diastolic blood pressure which is measured over few weeks or history of taking medication for elevated blood pressure has considered as hypertension. The following categories are considered while labeling hypertension.

Categories of blood pressure	Systolic Blood Pressure (mmHg)		Diastolic Blood Pressure (mmHg)
Normal	<120	and	<80
Elevated BP	120-129	and	<80
Stage 1 Hypertension	130-139		80-89
Stage 2 Hypertension	≥ 140		≥ 90

## DYSLIPIDEMIA(Adult Treatment Panel III, 2001)

Patient has history of abnormal blood lipid profile or on treatment due to high blood lipid by a physician or current blood reports showing any of the following -

LDL Cholesterol..... $\geq$  100 mg/dl

Total Cholesterol..... $\geq$  200 mg/dl

HDL Cholesterol..... $\leq$  40 mg/dl.

Serum Triglycerides..... $\geq$  150 mg/dl

## OBESITY AND OVERWEIGHT

Overweight and obesity are defined as abnormal or excessive fat accumulation that may impair health.

Body mass index (BMI) is a simple index of weight-for-height that is commonly used to classify overweight and obesity in adults. It is defined as a person's weight in kilograms divided by the square of his height in meters (kg/m^2).

According to the WHO definition for Asian population (Who expert consultation, 2004):

- BMI greater than or equal to 23 is overweight
- BMI greater than or equal to 25 is obesity.

